3.2.1 Hierarchical Analysis of Selected Secondary Endpoints

A hierarchical analysis will be performed in the order listed for the following secondary efficacy endpoints at Week 6 after Treatment 1:

- 1) Proportion of subjects with no episodes of UI (i.e. continence is achieved):
 - measured by 7-day bladder diary.
- 2) Mean change from study Baseline (assessed at Screening) in the I-QoL total summary score:
 - measured by patient-reported questionnaire.

3.3 Safety Variables

Safety will be assessed throughout the study by evaluating:

- Treatment Emergent Adverse Events (TEAEs)
- Adverse events of special interest (AESI)

- Adverse events (AEs) related to toxin spread
- AEs related to hypersensitivity
- Other protocol defined TEAEs
 - Urinary Tract Infections (UTI)
- Vital signs (heart rate, respiratory rate, blood pressure and body temperature)
- Laboratory blood parameters (haematology and serum chemistry)
- Laboratory urine parameters (laboratory urinalysis/microscopy, culture and sensitivity)
- Development of BTX-A antibodies (neutralizing)
- Usage of concomitant medications and therapies.

Timepoints for safety evaluations are detailed in [Appendix V](#).

4 PHARMACOKINETIC/PHARMACODYNAMIC VARIABLES

Not applicable.

5 ANALYSIS POPULATIONS

5.1 Screened Population

Screened population includes all subjects screened (enrolled); these are subjects who have signed the informed consent.

5.2 Randomised Population

All subjects assigned a randomisation number. Randomised subjects will be analysed according to their randomised treatment.

5.3 Safety Population

All subjects who received at least one IMP administration (including only partial administration) of the IMP. Safety subjects will be analysed according to their actual treatment received.

5.4 Modified Intention-to-Treat Population

All randomised subjects who received at least one IMP administration. Modified intention-to-treat (mITT) subjects will be analysed according to randomised treatment.

5.5 Per Protocol Population

All subjects in the mITT population who have no important protocol deviations that could potentially affect the primary efficacy endpoint outcome for the subject. Per Protocol (PP) subjects will be analysed according to the randomised treatment.

5.5.1 Protocol Deviations

Protocol deviations are defined as any change, divergence, or departure from the study design or procedures defined in the study protocol. Important protocol deviations are a subset of protocol deviations that may significantly impact the correctness, accuracy, and/or reliability of the study data or that may significantly affect a subject's rights, safety, or well-being. A detailed list of protocol deviations that will be mapped to protocol deviation coded term based

on Ipsen SDTM+ User Guide are contained in the separate document titled “Ipsen 222 and 223: Protocol Deviations”; this will be standalone working document which will be finalised prior to database lock.

5.5.1.1 Important Protocol Deviations Leading to Exclusion from the PP Analysis

Only those important protocol deviations considered to have a major effect on primary efficacy analysis will lead to complete exclusion of the patient from the PP population. The majority of the important protocol deviations leading to exclusion from the PP population will be determined programmatically from the data. Those criteria which require clinical or medical monitoring interpretation will be reviewed prior to database lock these will be outlined in the “Ipsen 222 and 223: Protocol Deviations” document.

5.5.1.2 Handling of Stratification Factors

Stratification errors (e.g. previous intradetrusor BTX-A usage) discovered after randomisation cannot be changed in the IVRS system and subjects will be analysed according to their eCRF recorded strata (i.e. correct strata) for the primary analysis of efficacy.

Mis-stratifications will be documented as a protocol deviation, and the incorrect stratification recorded in Interactive Voice Response System (IVRS) (NDO medical history for aetiology of NDO [SCI or MS], and prior medications for previous intradetrusor BTX-A usage for UI [BTX-A naïve or BTX-A non-naïve] in the bladder) will be used to perform a sensitivity analysis on the primary endpoint. A listing with the eCRF versus IVRS recorded stratifications will be displayed for the randomised subjects.

5.6 Urodynamic Population

All subjects in the mITT population included in the urodynamic subset at randomisation.

6 DATA HANDLING

6.1 Time points and Visit Windows

Day 1 is defined as the day of the first IMP administration. Relative days after Day 1 are calculated as (assessment date - Day 1 date) + 1. Relative days prior to Day 1 are calculated as (assessment date - Day 1 date). The day prior to Day 1 is Day -1.

Generally, all analysis will be performed using data at nominal visits (see [Table 1](#)). Only if the data is missing, the unscheduled visits (or early withdrawal visit) within the visit window will be used in analysis of efficacy endpoints. For the 7-day bladder diary, the entire 7-day duration need not be included in the entire visit window for it to be assigned to that visit e.g. if a patient has start date of the 7-day bladder diary on Day 61, then the 7th day would fall on Day 67, and would be assigned to Week 6 diary data.

If multiple unscheduled visits occur within a single visit, then the unscheduled visit closest to the target day of the visit window will be used in the analysis. If there is a tie, the later unscheduled visit will be used in the analysis. Similarly, if there are both scheduled and unscheduled visits prior to Treatment 1 then the last assessment prior to the Treatment 1 will be used as baseline in analysis of efficacy endpoints.

Statistical Analysis Plan

Version: Final v1.0

Date of Issue: 21-

September-2018

Ipsen Protocol No. D-FR-52120-223

Covance Study ID:

000000146513

Table 1 Definition of Visit Windows

Visit	Target Day of Visit ^a	Acceptable visit window mITT/PP/urodynamic analyses
Screening	Day -30	NA
Treatment visit of DBPC cycle	Day 1	NA
Week 2	Day 15	Days 8 to 22 (Day 15±7 days)
Week 6	Day 43	Days 23 to 63 (Day 43±20 days)
Week 12	Day 85	Days 64 to 106 (Day 85±21 days)
Week 24	Day 169	Days 107 to 211 (Day 169-62 days and +42 days)
Week 36	Day 253	Days 212 to 295 (Day 253-41 days and +42days)
Routine visit every 12 weeks until retreatment occurs or EOS	Day x + 84	Day x-41 days and Day x +42days)
End of Study^b (Week 104)	Day X	Day X±14 days
Retreatment Assessment Visit		Within 14 days of request
Retreatment Visit of treatment cycle 2 ^c	Day 1	Within 14 days of confirmed eligibility.
Week 2	Day 15	Days 8 to 22 (Day 15±7 days)
Week 6	Day 43	Days 23 to 63 (Day 43±20 days)
Week 12	Day 85	Days 64 to 106 (Day 85±21 days)
Week 24	Day 169	Days 107 to 211 (Day 169-62 days and +42 days)
Week 36	Day 253	Days 212 to 295 (Day 253-41 days and +42days)
Routine visit every 12 weeks until retreatment occurs or EOS	Day x + 84	Day x-41 days and Day x +42days)
End of Study^b (Week 104 to Week 116)	Day X	Day X ±14 days

^a Relative to the date of the first IMP administration (Day 1) of DBPC Cycle

^b The EOS visit will occur at Week 104 for subjects who had their most recent IMP administration at Week 92 or earlier.

^c The visit window from treatment cycle 3, 4, 5, etc. is the same as treatment cycle 2.

6.2 Handling of Dropouts or Missing Data

6.2.1 Analysis Endpoints

6.2.1.1 Efficacy Endpoints

Refer to Section 3.1 and 3.2 for the list of primary and secondary efficacy endpoints and Section 3.2.1 for the list of secondary endpoints used in the hierarchical analysis.

Bladder diary: For data collected from the 7-day bladder diary, if there is 1 or 2 days with no data, the arithmetic means recorded (on the 5 or 6 days that do have events recorded) from the bladder diary parameters will be used for the days with no recorded bladder diary data. If there are more than 2 days of missing data, then the 7-day bladder diary data will be considered invalid.

Statistical Analysis Plan

Version: Final v1.0
September-2018

Ipsen Protocol No. D-FR-52120-223
000000146513

Date of Issue: 21-

Covance Study ID:

Primary efficacy endpoint: No imputation is planned for the primary analysis of the primary endpoint. A sensitivity analysis of the primary efficacy endpoint will be performed using multiple imputations (MI) for missing or invalid data (see Section 7.6.4.3).

Urodynamic secondary efficacy endpoints: All urodynamic data will be reviewed by independent central reviewers to determine the final values for the urodynamic parameters. Only the central reader urodynamic values will be used for analysis purposes. For the secondary efficacy endpoint of Vol@1stIDC, subjects who do not exhibit a post-treatment IDC after the first IMP administration will have Vol@1stIDC imputed using the recorded corrected MCC volume at that post-treatment visit.

Quality of life secondary endpoints: For I-QoL total summary score, in accordance with the I-QoL User's Manual (US English version, March 2013), if no more than three items are omitted, a normal arithmetic mean substitution will be computed for these omitted items and imputed to calculate the total summary score. If more than three items are omitted, then there will be no more imputation for those omitted items, and the total summary score will be missing. Similarly, this rule will be applied for each of the domain scores (avoiding and limiting behavior, psychosocial impact, and social embarrassment). These derived scores will be used for analysis, and the investigator recorded eCRF I-QoL total summary score, and each recorded domain score will only be listed.

The formula for the derived scale scores is as follows:

$$\text{Scale Score} = \left\{ \frac{\text{(the sum of the items - lowest possible score)}}{\text{possible raw score range}} \right\} * 100$$

For continuous endpoints analysed by mean or mean change values, inference will be done using mixed-models repeated measures, which assumes that missing outcomes are missing at random (MAR).

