**PAGE 34/139** 

### 3 STUDY DESIGN

# 3.1 General Design and Study Schema

This is a phase III, multicentre, randomised, double blind, parallel group, placebo controlled study to assess the efficacy and safety of two doses of Dysport® (600 U and 800 U) in adult subjects with SCI or MS with UI due to NDO, who have not been adequately managed with oral medication and who routinely require CIC to manage their bladder function. The study will be conducted at approximately 90 study sites and 330 subjects are planned.

This study has two treatment periods:

- A double blind placebo controlled period, where subjects receive a single IMP treatment administration of either 600 U or 800 U Dysport® or placebo
- A subsequent double blind active treatment period, where subjects can receive multiple active IMP retreatment administrations of either 600 U or 800 U Dysport®. This second period commences when subjects receive their first study retreatment.

There is significant variability of local clinical practice in conducting urodynamic (filling cystometry) assessments. Due to the difficulties in standardising and performing study specific urodynamics in a global program, this study will include sites that are unable to alter their local site practice sufficiently to perform standardised urodynamics. The study therefore has two subsets:

- Urodynamic subset (planned ≥200 subjects)
  - All subjects in this subset must have standardised urodynamics (as described in the Study Specific Urodynamic Manual) during Screening and at Week 6 following each study treatment
  - o Screening standardised urodynamics must confirm the presence of NDO
- Non-Urodynamic subset
  - All subjects in this subset must have documented urodynamic proven NDO in the 12 months prior to Screening. If not, then urodynamics must be performed per local practice during Screening to confirm the diagnosis of NDO
  - o Urodynamics will not be performed in the post-screening period in this subset

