# 3.2.2 Secondary Efficacy Endpoints and Evaluations

# 3.2.2.1 Overview of Secondary Measures

Mean change from study Baseline (assessed at Screening) or from treatment cycle baseline (assessed at Retreatment Assessment Visit) to post-treatment timepoints (timepoints listed in Table 4 and Table 5):

- Bladder diary measures:
  - weekly number of UI episodes
  - daily urinary frequency (total, spontaneous void only, CIC only)
  - 24-hour voided volume (total, spontaneous void only, CIC only)
  - volume per void (total, spontaneous void only, CIC only).
  - Urodynamic filling cystometry measures (urodynamic subset only):
    - maximum cystometric capacity (MCC)
    - maximum detrusor pressure (MDP) during storage
    - volume at first involuntary detrusor contraction (Vol@1stIDC) (subjects without a post-treatment IDC will have their Vol@1stIDC imputed from their MCC)
    - maximum detrusor pressure at first involuntary detrusor contraction (PdetMax@1stIDC)
    - end fill pressure (EFP)
    - detrusor compliance (DC).
- Patient-reported outcome questionnaires:
  - incontinence quality of life (I-QoL) total summary score
  - EuroQol 5-dimension 5-level (EQ-5D-5L)
  - modified patient global impression improvement (mPGI-I) score (to be assessed at each timepoint without comparison to baseline).

Proportion of subjects at post-treatment timepoints following the first and subsequent treatments with:

- no episodes of UI (i.e. continence is achieved)
- UI response at several levels (i.e. ≥30% improvement, ≥50% improvement, ≥75% improvement etc.)
- no IDCs on urodynamic assessment (i.e. urodynamic cure is achieved) (urodynamic subset only).

Duration of effect following the first and subsequent treatments measured by:

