**PAGE 91/139** 

Parameter	Unit	Calculation	
MCC	mL	Total instilled volume or instilled volume just prior to the terminal IDC	
		minus	
		incontinent volume	
MDP	cm H 2 O	Peak detrusor pressure during storage (filling) phase	
		minus	
		trace baseline pressure	
Presence of IDC(s)	N/A	N/A	
Vol@1stIDC	mL	Instilled volume when first IDC commences	
PdetMax@1stIDC	cm H 2 O	Peak detrusor pressure during first IDC	
		minus	
		trace baseline pressure	
EFP	cm H 2 O	Detrusor pressure at end of filling or just prior to the terminal IDC	
		minus	
		trace baseline pressure	
DC	mL/cm H 2 O	Change in bladder volume	
		divided by	
		change in detrusor pressure	
		(usually measured as MCC divided by EFP)	

Table 20 Urodynamic Parameters

DC=detrusor compliance; EFP=end fill pressure; IDC=involuntary detrusor contraction; MCC=maximum cystometric capacity; MDP=maximum detrusor pressure; PdetMax@1stIDC=maximum detrusor pressure at first involuntary detrusor contraction; Vol@1stIDC=volume at first involuntary detrusor contraction.

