3.2 Secondary Efficacy Endpoints

The secondary efficacy endpoints are divided into those that relate to parameters measured in the bladder diary, those measured by urodynamic filling cystometry and those that are quality of life measures. From these secondary measures, there are two that have been selected to be analysed as part of a hierarchical testing scheme see Section 3.2.1.

Bladder diary measures:

Mean change from study baseline to post-treatment timepoints in the following variables:

- weekly number of UI episodes (except for week 6 after Treatment 1 which is the primary efficacy endpoint)
- total daily urinary frequency (spontaneous void and CIC)
- daily spontaneous voiding frequency
- daily CIC frequency
- total 24-hour voided volume (spontaneous void and CIC)
- 24-hour voided volume (spontaneous void only)
- 24-hour voided volume (CIC only)
- total volume per void (spontaneous void and CIC)
- volume per void (spontaneous void only)
- volume per void (CIC only)

Proportion of subjects with:

- no episodes of UI (i.e. 100% improvement where continence is achieved)
- UI response at several levels (i.e. $\geq 30\%$ improvement, $\geq 50\%$ improvement, $\geq 75\%$ improvement)

Urodynamic filling cystometry measures (urodynamic subset only):

Mean change from study baseline to week 6 after Treatment 1 in the following variables:

- MCC
- MDP during storage
- Vol@1stIDC (subjects without a post-treatment IDC will have their Vol@1stIDC imputed from their MCC)
- maximum detrusor pressure at first involuntary detrusor contraction (PdetMax@1stIDC)

- end fill pressure (EFP)
- detrusor compliance (DC)

Proportion of subjects with:

- No IDCs (i.e. urodynamic cure is achieved)

Patient-reported outcome questionnaires:

Mean change from study baseline to post-treatment timepoints in the following variables:

- I-QoL total summary score
- I-QoL Score of domain: Avoidance and limiting behaviour
- I-QoL Score of domain: Psychosocial impact
- I-QoL Score of domain: Social embarrassment
- EuroQol 5-dimension 5-level (EQ-5D-5L): Total descriptive score
- EQ-5D-5L: self-rated health (VAS)
- modified patient global impression - improvement (mPGI-I) score (to be assessed at each timepoint without comparison to baseline)

Duration of effect following the first and subsequent treatments

- time to request retreatment
- time to eligibility for retreatment
- time between treatments.

Detailed definitions of all efficacy endpoints are presented in [Appendix II](#).

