7.6.6.2 Urodynamic Filling Cystometry Parameters

See Section 3.2 for list of urodynamic endpoints.

The summary tables for mean values at Week 6 and the mean change from study baseline for the DBPC cycle, and for the Dysport Cycles (i.e. Dysport Cycle 1, Dysport cycle 2 ...) will be presented using descriptive statistics for continuous endpoints. For each of the “mean change” at Week 6 urodynamic parameters, an ANCOVA model will be fitted using the “mean change” endpoint, as the response variable to obtain the p-value of treatment groups. The model will be the same as the sensitivity analyses for the primary efficacy endpoint in 7.6.4.2. The LSMEANS of the mean change from study baseline at Week 6 in each group with standard error, the difference of mean between the two treatment groups, the 95% CI of the difference and the p-value for treatment group will be presented.

Number and percentage of subjects with no IDC will be also summarised. A logistic regression model will be performed with “proportion of subjects” as the response variable. The model will include treatment group, and stratification variables.

Odds ratio, 95% CI of odds ratio, and p-value will be presented.

The SAS codes of logistic regression for reference are below.

CCI
[Redacted SAS code block]

In above codes, the variables are defined as:

Statistical Analysis Plan

Version: Final v1.0

Date of Issue: 21-

September-2018

Ipsen Protocol No. D-FR-52120-223

Covance Study ID:

000000146513

CCI

Line plots of the LS means of changes will be plotted for MCC, MDP, Vol@1stIDC. In addition, a bar chart for the proportion of subjects with no IDC at Week 6 will be plotted.

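### In subjects with no involuntary detrusor contraction, volume at first contraction is imputed on a net-of-leak scale although the endpoint is a gross instilled volume; the effect is probably small and confined to those who leak

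*SAP*

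**What the plan says.** Protocol 7.3.2.1, Table 20, gives the two definitions that matter. Vol@1stIDC is "Instilled volume when first IDC commences", with no deduction. MCC starts from "Total instilled volume or instilled volume just prior to the terminal IDC" and then subtracts "incontinent volume".

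SAP 3.2 states the imputation in short form: "subjects without a post-treatment IDC will have their Vol@1stIDC imputed from their MCC". Protocol 3.2.2.1 has the same rule. SAP 6.2.1.1 adds one word: such a subject "will have Vol@1stIDC imputed using the recorded corrected MCC volume at that post-treatment visit".

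At entry to the urodynamic subset, "Screening standardised urodynamics must confirm the presence of NDO" (Protocol 3.1), and Protocol 7.3.2.1 judges this by the presence of IDCs. The baseline Vol@1stIDC is therefore normally an observed, gross volume. For the analysis, SAP 7.6.6.2 says: "For each of the “mean change” at Week 6 urodynamic parameters, an ANCOVA model will be fitted". The visible text has no step that adds leaked volume back, no censored-data method and no sensitivity analysis for this imputation.

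**The concern.** Observed values of Vol@1stIDC are gross instilled volumes; imputed values are net of leakage. Both enter the same ANCOVA as one variable. For an IDC-free subject who leaked, the change score takes a gross baseline from a net Week 6 value. The subject can then be given a figure below an instilled volume at which absence of an IDC was actually observed.

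At stake is the estimated treatment effect on one urodynamic endpoint. Being IDC-free is the favourable outcome, and the understatement falls only on those who reach it. If that outcome is commoner on Dysport, the difference from placebo is pulled toward zero.

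**Working it through.** The plan states no figure for this imputation, so there is none to reproduce. The check is algebra on the Table 20 definitions, followed by a size calculation on assumed inputs.

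**Step 1: shortfall per subject.** Let V be the total instilled volume and L the leaked volume in a subject with no IDC.

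- Instilled volume shown to be free of IDC: V. The true first-IDC volume lies above V.
- Imputed value: MCC = V − L.
- Shortfall against V: V − (V − L) = L, which is zero only if L = 0.

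For an illustrative V of 400 mL:

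| L (mL) | Imputed now (mL) | Imputed from gross volume (mL) |
|---|---|---|
| 0 | 400 | 400 |
| 25 | 375 | 400 |
| 50 | 350 | 400 |
| 100 | 300 | 400 |
| 150 | 250 | 400 |

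**Step 2: ordering.** Take two subjects, each filled to 400 mL and each having leaked 60 mL on the way. Subject A has a first IDC at 400 mL and is recorded as 400 mL. Subject B has no IDC, the better result, and is imputed 400 − 60 = 340 mL. If A's IDC is also the terminal one, A's own MCC is 400 − 60 = 340 mL. The same filling thus gives 400 on one scale and 340 on the other.

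**Step 3: effect on the treatment difference.** Let pD and pP be the IDC-free shares on Dysport and placebo, q the share of IDC-free subjects who leak, and L their mean leak, with q and L taken as equal across arms.

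- Fall in an arm mean = p × q × L.
- Fall in the difference = (pD − pP) × q × L.

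The rule leaves baseline unchanged, so under randomisation this is also, in expectation, approximately the shift in the ANCOVA-adjusted difference.

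None of pD, pP, q or L is in the documents. Assumed ranges: pD 0.30 to 0.60, pP 0.05 to 0.10, q 0.10 to 0.50, L 25 to 100 mL.

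| Case | pD, pP, q, L | Dysport mean falls by | Placebo mean falls by | Difference falls by |
|---|---|---|---|---|
| No leak | any, q × L = 0 | 0 | 0 | 0 |
| Low | 0.30, 0.05, 0.10, 25 | 0.75 mL | 0.125 mL | 0.625 mL |
| Few leak | 0.45, 0.05, 0.10, 50 | 2.25 mL | 0.25 mL | 2.0 mL |
| More leak | 0.45, 0.05, 0.30, 50 | 6.75 mL | 0.75 mL | 6.0 mL |
| High | 0.60, 0.10, 0.50, 100 | 30 mL | 5 mL | 25 mL |

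**Step 4: scale.** The protocol plans no difference for Vol@1stIDC. Table 21 gives a standard deviation of 212.9 mL for MCC, a different endpoint, used here only for orientation. Against it, 0.625 / 212.9 = 0.003 SD, 2.0 / 212.9 = 0.009 SD, 6.0 / 212.9 = 0.03 SD and 25 / 212.9 = 0.12 SD.

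**The case against.** **Leakage without an IDC may be uncommon.** Protocol 1.1.1 attributes the incontinence of this condition to IDCs. On that account most leakage occurs in subjects who have IDCs, to whom the imputation does not apply. This stands, and it is the main reason to expect a small effect. It does not make the effect zero, and the documents give no frequency.

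**Net volume is closer to what the bladder held.** If fluid escapes during filling, the bladder never contained V, and a gross figure credits fluid already lost. This stands as a cost of the fix. It does not rescue the rule, because observed values and the normally IDC-positive baseline are not leak-corrected. If net volume is preferred, observed values need the same correction.

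**Unseen sources may settle it.** SAP Appendix II is not visible, and the separate urodynamic manual was not available. Either could say how leakage is handled for Vol@1stIDC. That reservation stands.

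**The endpoint is exploratory.** Protocol 9.6 lists Vol@1stIDC third in an ordered urodynamic set but leaves the method to the SAP. SAP 7.6.2 and 7.6.6 treat every secondary endpoint outside the two-endpoint hierarchy (continence and I-QoL) as exploratory. This stands.

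A reader might infer that the word corrected in SAP 6.2.1.1 departs from the protocol. The documents do not support that: MCC in Table 20 is already net of leakage, so the three statements of the rule agree and the scale problem arises without that word.

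**Conclusion.** The scale mismatch is real and follows from Table 20. In an IDC-free subject who leaks during filling, the imputed Vol@1stIDC is too low by the leaked volume; in one who does not leak, the rule returns the gross volume and there is no scale error.

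The effect is probably small but cannot be sized from the documents. The 0.6 to 25 mL range for the treatment difference rests wholly on assumed inputs, and its upper end needs half of IDC-free subjects to leak 100 mL each. The direction, toward zero, holds if IDC-free status is commoner on Dysport and leakage among IDC-free subjects is similar across arms.

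Three stronger readings are tempting and not supported. The first is that all imputed values are on the wrong scale; only those from subjects who leak are. The second is that a confirmatory claim or the type I error is at risk; the primary endpoint, the sample size and alpha are untouched, and the SAP makes no confirmatory claim on Vol@1stIDC. The third is that the gross volume would recover the true value; that value is right-censored at V, so V is still only a lower bound. This is a minor, optional improvement to a derivation.

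**What to change.** - In SAP 6.2.1.1, and in SAP 3.2 to match, impute Vol@1stIDC in IDC-free subjects with the total instilled volume at end of filling, that is, the MCC term before leaked volume is subtracted.
- Record the departure from Protocol 3.2.2.1 in SAP section 8, which currently lists no changes.
- Keep the corrected-MCC value as a sensitivity analysis.

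SAP section 1 allows amendments finalised before database lock, so this can be done by amending the SAP.

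Costs:

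- The uncorrected volume must be available from the central reading. Computing MCC under Table 20 requires it, but the SAP mentions only the recorded corrected volume, so its presence in the analysis data needs checking.
- The gross figure credits fluid no longer in the bladder; the sensitivity analysis shows how much this matters.
- The imputed value remains a lower bound, and the report should say so.
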